12 DISCONTINUATION AND REPLACEMENT OF SUBJECTS

12.1 Early Discontinuation of Study Drug

A subject may be discontinued from study treatment at any time if the subject, the investigator, or the Sponsor feels that it is not in the subject’s best interest to continue. The following is a list of possible reasons for study treatment discontinuation:

- Subject withdrawal of consent (or assent)
- Subject is not compliant with study procedures
- Adverse event that in the opinion of the investigator would be in the best interest of the subject to discontinue study treatment

- Protocol violation requiring discontinuation of study treatment
- PI request for early termination of study

If a subject is withdrawn from treatment due to an adverse event, the subject will be followed and treated by the Investigator until the abnormal parameter or symptom has resolved or stabilized.

All subjects who discontinue study treatment should come in for an early discontinuation visit as soon as possible and then should be encouraged to complete all remaining scheduled visits and procedures.

All subjects are free to withdraw from participation at any time, for any reason, specified or unspecified, and without prejudice.

Reasonable attempts will be made by the investigator to provide a reason for subject withdrawals. The reason for the subject's withdrawal from the study will be specified in the subject's source documents Refer to Section 10 for early termination procedures.

12.2 Withdrawal of Subjects from the Study

A subject may be withdrawn from the study at any time if the subject, the investigator, or the Sponsor feels that it is not in the subject's best interest to continue.

All subjects are free to withdraw from participation at any time, for any reason, specified or unspecified, and without prejudice.

Reasonable attempts will be made by the investigator to provide a reason for subject withdrawals. The reason for the subject's withdrawal from the study will be specified in the subject's source documents. As noted above, subjects who discontinue study treatment early (i.e., they withdraw prior to 1) should have an early discontinuation visit. Refer to Section 10 for early termination procedures. Subjects who withdraw after Visit 1 but prior to Visit 2 should be encouraged to come in for a final visit (and the procedures to be followed would include those for their next scheduled visit).

12.3 Replacement of Subjects

Subjects who withdraw from the study treatment will not be replaced.

Subjects who withdraw from the study will not be replaced.

13 PROTOCOL VIOLATIONS

A protocol violation occurs when the subject, investigator fails to adhere to significant protocol requirements affecting the inclusion, exclusion, subject safety and primary endpoint criteria. Protocol violations for this study include, but are not limited to, the following:

- Failure to meet inclusion/exclusion criteria
- Use of a prohibited concomitant medication

Failure to comply with Good Clinical Practice (GCP) guidelines will also result in a protocol violation. The PI will determine if a protocol violation will result in withdrawal of a subject.

When a protocol violation occurs, it will be discussed with the investigator and a Protocol Violation Form detailing the violation will be generated. This form will be signed by a Sponsor representative and the Investigator. A copy of the form will be filed in the site's regulatory binder and in the Sponsor's files.

14 STATISTICAL METHODS AND CONSIDERATIONS

Prior to the analysis of the final study data, a detailed Statistical Analysis Plan (SAP) will be written describing all analyses that will be performed. The SAP will contain any modifications to the analysis plan described below.

14.1 Data Sets Analyzed

All eligible patients who are randomized into the study and receive the only one dose of the study dietary supplement (the Safety Population) will be included in the safety analysis.

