4 STUDY DESIGN

4.1 Study Overview

This is a single center, double-blind, placebo-controlled, randomized study. 30 (number) of subjects are planned. Because the study only investigating the acute effect of the study interventional product, each subject will be administered a single dose of either study dietary supplement or placebo only one time. Subjects will be assigned to the treatments in random order. Evaluations will be taken at baseline and every 30 min following the ingestion of carbohydrates for the following 2 hours at the interval of 30, 60, 90, 120 min.

Screening data will be reviewed to determine subject eligibility. Subjects who meet all inclusion criteria and none of the exclusion criteria will be entered into the study.

The following treatment regimens will be used:

- A dietary supplement E.cava extracted capsule (seaweed) - at dose of 580 mg.
- Placebo (dextrin) – at a dose of 500 mg.

Total duration of subject participation will be six weeks. Total duration of the study is expected to be 12 weeks.

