8 STUDY TREATMENTS

8.1 Method of Assigning Subjects to Treatment Groups

Up to 30 eligible patients will be randomly assigned to the dietary supplement seaweed or placebo treatment groups in a 1:1 ratio using a SAS-based computer-generated randomization scheme developed by a study investigator who will not be involved in data collection and analysis. Participants and other investigators will be blinded to which supplement is consumed each testing occasion for each participant until data analysis completed. At screening visit investigators will complete patient required data as detailed in the Study Manual, and fax it to the investigator who is responsible for randomization. The investigator who responsible for randomization will send back participants data encoded with numbers and supplements (intervention & placebo) with letters (A, B). Study intervention or placebo will be encapsulated in identical capsules and will be labelled with the letter A and B to conceal which supplement is given to each participants.

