8.4.3 Administration Instructions

The study dietary supplement (seaweed) or placebo will be administered to patient at the study site only one time at a supervision of study investigator and medical monitor where the patient will be instructed to administer the study capsules orally.

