10 EVALUATIONS BY VISIT

10.1 Visit 1 (Day1 /Week 1/Month 1)

1. Review the study with the subject (subject's legal representative) and obtain written informed consent.
2. Assign the subject a unique screening number.
3. Record demographics data.
4. Record medical history, including a history of pre-diabetic, diagnosis date.
5. Perform a complete physical examination.
6. Perform and record vital signs.
7. Perform and record results of blood pressure testing.
8. Collect blood for clinical laboratory tests (baseline of blood glucose level).
9. Schedule subject for Visit 2 in different days.
10. List all additional procedures, such as Randomize subject

10.2 Visit 2

1. Perform abbreviated physical examination.
2. Perform and record vital signs.
3. Collect blood for clinical laboratory tests (baseline of blood glucose and insulin levels).
4. Administer either study dietary supplement (seaweed) or placebo based on blinded randomization.
5. Perform carbohydrates ingestion
6. Collect blood for clinical laboratory tests (blood glucose and insulin levels 30 min after administration of study treatment).
7. Collect blood for clinical laboratory tests (blood glucose and insulin levels 60 min after administration of study treatment).
8. Collect blood for clinical laboratory tests (blood glucose and insulin levels 90 min after administration of study treatment).
9. Collect blood for clinical laboratory tests (blood glucose and insulin levels 120 min after administration of study treatment).

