14.3 Analysis of Primary Endpoint

Mean (standard deviation) will be reported for normally distributed data, whereas median (interquartile range) will be reported for not normally distributed data. Either independent t-test or Mann-Whitney test, based on normality of data, will be used to determine the difference between the two groups for both PPBG and PIL at a significant level of $p < 0.05$. Incremental area under the curve (iAUC), time to peak and peak blood concentration assessment will be used to assess postprandial responses of for plasma glucose and insulin level. Safety and tolerability data will be summarized by treatment group.

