14.4 Analysis of Secondary Endpoints

Mann-Whitney test will be used to determine differences for symptoms of intolerance between groups.

Adverse events will be tabulated by treatment group and will include the number of patients for whom the event occurred, the rate of occurrence, and the severity and relationship to study drug.

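### The Safety Population in section 14.1 is worded around the seaweed product and around eligibility, which conflicts with the plan's own by-group safety analyses and could let a dosed participant be left out

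*Combined protocol and SAP*

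**What the plan says.** Section 14.1 (Data Sets Analyzed) gives one definition and no other analysis set: "All eligible patients who are randomized into the study and receive the only one dose of the study dietary supplement (the Safety Population". This group enters the safety analysis.

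The sections that describe dosing set that product against placebo:

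- Section 4.1: "each subject will be administered a single dose of either study dietary supplement or placebo only one time".
- Section 8.4.3: "The study dietary supplement (seaweed) or placebo will be administered to patient at the study site only one time". Section 8.7 uses the same pairing.
- Section 10.2 (Visit 2): "Administer either study dietary supplement (seaweed) or placebo based on blinded randomization".

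The safety analyses are comparative. Section 3.2 states the secondary objective as safety against placebo. Section 14.3 says "Safety and tolerability data will be summarized by treatment group". Section 14.4 says "Adverse events will be tabulated by treatment group" and adds a Mann-Whitney test of intolerance symptoms between groups.

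On eligibility, section 13 lists failure to meet the inclusion or exclusion criteria among the protocol violations and leaves withdrawal of the subject to the principal investigator.

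**The concern.** A safety set normally contains everyone who was exposed to a study product. The wording in 14.1 adds two conditions that do not belong there.

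The first is receipt of a product that the dosing sections identify as seaweed. Followed to the letter, it leaves the by-group tables in 14.3 and 14.4 without a control column. A programmer would have to depart from 14.1 to produce them.

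The second is eligibility, and it matters more because nothing else in the plan corrects it. The schedule makes late discovery of ineligibility possible:

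- Section 10.1 and Appendix 1 put both the first glucose sample and randomisation at Visit 1.
- Appendix 1 repeats fasting glucose at Visit 2, the dosing visit.
- Appendix 1 lists concomitant medication review only at Visit 2, whereas section 9.1.1 places it at baseline/screening. Anti-diabetic drugs are an exclusion under 6.3.

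Section 5.3 counts glucose above 240 or below 70 mg/dl as a safety finding. A participant who was out of the fasting range or on a glucose-lowering product is a plausible source of such a finding, and is also the one whom the wording would allow an analyst to leave out.

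**Working it through.** The plan gives no size for the Safety Population. Its one related calculation, the sample size in 14.6, reproduces: 2 × 32² × (1.96 + 0.84)² / 38² = 16056.32 / 1444 = 11.12, rounded up to 12 per group. The point here does not depend on it.

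**Inputs.** Section 8.1: "Up to 30 eligible patients will be randomly assigned to the dietary supplement seaweed or placebo treatment groups in a 1:1 ratio". So 30 / 2 = 15 per arm. Assume that all 30 are dosed. Let *k* be the number of dosed participants later found ineligible, all in the seaweed arm for illustration. The documents give no value for *k*.

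**Size of the set under three wordings**

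| *k* | 14.1 to the letter (15 − *k*) | Both arms, eligible only (30 − *k*) | All who receive a capsule |
|---|---|---|---|
| 0 | 15 (0 on placebo) | 30 | 30 |
| 1 | 14 (0 on placebo) | 29 | 30 |
| 2 | 13 (0 on placebo) | 28 | 30 |
| 3 | 12 (0 on placebo) | 27 | 30 |

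The first column cannot be combined with 14.3 and 14.4, which need placebo data. The second is the realistic reading if *eligible* is applied after the fact. The third is what a safety set should be.

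**Weight of one removal.** 1 / 15 = 6.7% of an arm. If the removed participant had the arm's only event, the reported rate moves from 1/15 = 6.7% to 0/14 = 0%. If the arm had two events and one is removed, it moves from 2/15 = 13.3% to 1/14 = 7.1%.

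**Timing.** Section 14 promises a detailed SAP before the final analysis. Section 14.5 places a safety interim at about 50% of patients, or about 15 of 30, so it could be run while 14.1 is still the only definition.

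**The case against.** Three replies have force.

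*The term is not used uniformly.* Section 8.1 writes "supplements (intervention & placebo) with letters (A, B", so supplement there covers both products. Sections 8.5 and 8.5.1, on supply and storage, use study dietary supplement where all trial product seems to be meant. Read with 3.2, 14.3 and 14.4, section 14.1 makes sense only if it includes both arms. This stands. A reader might infer that the plan discards 15 of 30 participants and leaves the secondary objective without a comparator; the documents do not support that. The by-group analyses show the intent, and no section ties the Mann-Whitney test of symptoms to the Safety Population. What remains is that the dosing sections, which are closest in meaning to receiving a dose, consistently use the term for seaweed.

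*Eligibility is settled before randomisation.* Section 4.1 enters only subjects who satisfy the criteria, and 8.1 randomises eligible patients, so 14.1 may simply repeat that sequence. Withdrawal under section 13 is also not exclusion from an analysis. This is a fair reading, but 14.1 does not choose it, and no section returns a dosed, ineligible participant to the set.

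*Events are recorded anyway.* Sections 9.1.6 and 11.1 capture adverse events throughout, and 11.2.1 documents all serious events and sends them to the ethics board. A reader might infer that the wording hides events; it does not. What is at risk is whether they appear in the tabulated rates and denominators.

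The later SAP can make the correction, but the current text does not yet do so.

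**Conclusion.** The point holds as a wording defect with two parts. The placebo part is an internal conflict whose intended resolution is clear; the loss of the placebo arm is only a literal reading and not an expected outcome. The eligibility part is the more substantive, because the text admits two readings and one of them permits removal of an exposed participant. Its size is 6.7% of an arm per removal, assuming 15 per arm and all dosed; the frequency is unknown and may be zero. No error rate, power or sample-size figure changes.

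**What to change.** Reword 14.1 to: *The Safety Population is all randomised participants who receive the study capsule (seaweed or placebo), regardless of any later finding on eligibility, analysed by the product actually received.* Carry the same sentence into the SAP, and settle it before the safety interim in 14.5. The closing clause is not needed to cure either defect. It completes the definition by stating the group in which each participant is counted.

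The cost is one sentence in each document. It needs no extra participants, data or procedures.

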14.2 Demographic and Baseline Characteristics

- weight
- height
- BMI,
- age
- exercise level
- Collect blood for clinical laboratory tests (baseline of blood glucose level).

14.3 Analysis of Primary Endpoint

Mean (standard deviation) will be reported for normally distributed data, whereas median (interquartile range) will be reported for not normally distributed data. Either independent t-test or Mann-Whitney test, based on normality of data, will be used to determine the difference between the two groups for both PPBG and PIL at a significant level of $p < 0.05$. Incremental area under the curve (iAUC), time to peak and peak blood concentration assessment will be used to assess postprandial responses of for plasma glucose and insulin level. Safety and tolerability data will be summarized by treatment group.

14.4 Analysis of Secondary Endpoints

Mann-Whitney test will be used to determine differences for symptoms of intolerance between groups.

Adverse events will be tabulated by treatment group and will include the number of patients for whom the event occurred, the rate of occurrence, and the severity and relationship to study drug.

14.5 Interim Analysis

When approximately 50% of patients have completed the study through Visit 2, an interim analysis for safety will be conducted by an independent data monitoring committee. Serious adverse events will be monitored by the committee on an ongoing basis throughout the study.

14.6 Sample Size and Randomization

Sample size was calculated based in similar study (24) using sample size determination equation:

$$\frac{2SD^2(Z_{\alpha/2} + Z_B)^2}{d^2}$$

$$n = 2(32)^2(1.96+0.84)^2 / 38^2 = 2(1024) (2.8)^2 / 1444 = 2048*7.84 / 1444$$

$$= 16056.32 / 1444$$

$$= 11.11 \approx 12 \text{ subjects/group}$$

whereas:

- $Z_{\alpha/2}$ = standard normal variate for level of significant, at 5% type 1 error, (if $p < 0.05 = 1.96$).
- Z_B = Standard normal variate for power (for 80% power = 0.84, for 90% power = 1.28).
- SD= Standard Deviation (determined from the literature).
- d= effect size – difference between mean values (determined from the literature).

15 DATA COLLECTION, RETENTION AND MONITORING

15.1 Data Collection Instruments

The Investigator will prepare and maintain adequate and accurate source documents designed to record all observations and other pertinent data for each subject treated with the study drug.

Study personnel at the site will enter data from source documents corresponding to a subject's visit into the protocol-specific paper CRF when the information corresponding to that visit is available. Subjects will not be identified by name in the study database or on any study documents to be collected by the PI (or designee), but will be identified by a subject number

If a correction is made on a CRF, the study staff member will line through the incorrect data, write in the correct data and initial and date the change.

The Investigator is responsible for all information collected on subjects enrolled in this study. All data collected during the course of this study must be reviewed and verified for completeness and accuracy by the Investigator.

15.2 Data Management Procedures

The data will be entered into a validated database. The Data Management group will be responsible for data processing, in accordance with procedural documentation. Database lock will occur once quality assurance procedures have been completed.

All procedures for the handling and analysis of data will be conducted using good computing practices meeting FDA guidelines for the handling and analysis of data for clinical trials.

15.3 Data Quality Control and Reporting

After data have been entered into the study database, a system of computerized data validation checks will be implemented and applied to the database on a regular basis. Query reports (Data Clarification Requests) pertaining to data omissions and discrepancies will be forwarded to the Investigators and study monitors for resolution. The study database will be updated in accordance with the resolved queries. All changes to the study database will be documented.

15.4 Archival of Data

The database is safeguarded against unauthorized access by established security procedures; appropriate backup copies of the database and related software files will be maintained. Databases are backed up by the database administrator in conjunction with any updates or changes to the database.

At critical junctures of the protocol (e.g., production of interim reports and final reports), data for analysis is locked and cleaned per established procedures.

15.5 Availability and Retention of Investigational Records

The Investigator must make study data accessible to the monitor, other authorized representatives of the Sponsor (or designee), IRB/IEC, and Regulatory Agency (e.g., FDA) inspectors upon request. A file for each subject must be maintained that includes the signed Informed Consent, HIPAA Authorization and Assent Form and copies of all source documentation related to that subject. The Investigator must ensure the reliability and availability of source documents from which the information on the CRF was derived.

All study documents (patient files, signed informed consent forms, copies of CRFs, Study File Notebook, etc.) must be kept secured for a period of two years following marketing of the investigational product or for two years after centers have been notified that the IND has been discontinued. There may be other circumstances for which the Sponsor is required to maintain study records and, therefore, the Sponsor should be contacted prior to removing study records for any reason.

15.6 Monitoring

Monitoring visits will be conducted by representatives of the Sponsor according to the U.S. CFR Title 21 Parts 50, 56, and 312 and ICH Guidelines for GCP (E6). By signing this protocol, the Investigator grants permission to the Sponsor (or designee), and appropriate regulatory authorities to conduct on-site monitoring and/or auditing of all appropriate study documentation.

15.7 Subject Confidentiality

In order to maintain subject confidentiality, only a site number, subject number and subject initials will identify all study subjects on CRFs and other documentation submitted to the Sponsor. Additional subject confidentiality issues (if applicable) are covered in the Clinical Study Agreement.

16 ADMINISTRATIVE, ETHICAL, REGULATORY CONSIDERATIONS

The study will be conducted according to the Declaration of Helsinki, Protection of Human Volunteers (21 CFR 50), Institutional Review Boards (21 CFR 56), and Obligations of Clinical Investigators (21 CFR 312).

To maintain confidentiality, all laboratory specimens, evaluation forms, reports and other records will be identified by a coded number and initials only. All study records will be kept in a locked file cabinet and code sheets linking a patient's name to a patient identification number will be stored separately in another locked file cabinet. Clinical information will not be released without written permission of the subject, except as necessary for monitoring by the FDA. The Investigator must also comply with all applicable privacy regulations (e.g., Health Insurance Portability and Accountability Act of 1996, EU Data Protection Directive 95/46/EC).

16.1 Protocol Amendments

Any amendment to the protocol will be written by PI. Protocol amendments cannot be implemented without prior written IRB/IEC approval except as necessary to eliminate immediate safety hazards to patients. A protocol amendment intended to eliminate an apparent immediate hazard to patients may be implemented immediately, provided the IRBs are notified within five working days.

16.2 Institutional Review Boards and Independent Ethics Committees

The protocol and consent form will be reviewed and approved by the IRB/IEC of each participating center prior to study initiation. Serious adverse experiences regardless of causality will be reported to the IRB/IEC in accordance with the standard operating procedures and policies of the IRB/IEC, and the Investigator will keep the IRB/IEC informed as to the progress of the study. The Investigator will obtain assurance of IRB/IEC compliance with regulations.

Any documents that the IRB/IEC may need to fulfill its responsibilities (such as protocol, protocol amendments, Investigator's Brochure, consent forms, information concerning patient recruitment, payment or compensation procedures, or other pertinent information) will be submitted to the IRB/IEC. The IRB/IECs written unconditional approval of the study protocol and the informed consent form will be in the possession of the Investigator before the study is initiated. The IRB/IECs unconditional approval statement will be transmitted by the Investigator to PI prior to the shipment of study supplies to the site. This approval must refer to the study by exact protocol title and number and should identify the documents reviewed and the date of review.

Protocol and/or informed consent modifications or changes may not be initiated without prior written IRB/IEC approval except when necessary to eliminate immediate hazards to

the patients or when the change(s) involves only logistical or administrative aspects of the study. Such modifications will be submitted to the IRB/IEC and written verification that the modification was submitted and subsequently approved should be obtained.

The IRB/IEC must be informed of revisions to other documents originally submitted for review; serious and/or unexpected adverse experiences occurring during the study in accordance with the standard operating procedures and policies of the IRB; new information that may affect adversely the safety of the patients of the conduct of the study; an annual update and/or request for re-approval; and when the study has been completed.

